The in-office appliance utilized in our treatment will be fabricated by one operator (AN), and it will consist of a 0.022" slot MBT maxillary second molar mini tube that will be modified to have a tube length of 2 mm, and a 0.018" slot MBT maxillary canine bracket. The appliance will be fabricated using a 3d-printed model of the subject's maxillary arch. The maxillary second molar tube will be cemented on the center of the buccal surface of the maxillary first molar of the 3D-printed model. A 0.016x0.022" stainless steel wire with a bayonet bend positioned mesial to the maxillary first molar and a curve extending from the maxillary first molar to the maxillary canine will be placed, and it will guide the placement of the maxillary canine bracket, so that the stainless-steel wire can sit passively in both the molar tube and canine bracket slot. Once the maxillary canine bracket has been bonded, a pre-cut, closed-coil stainless-steel spring that spans from the mesial opening of the first molar tube to the distal wing of the canine bracket will be placed, and the wire will then be steel tied to the maxillary canine bracket, and then it will be cut and cinched mesial to the maxillary canine bracket. The wire will also be cinched 2-3 mm distal to the maxillary molar tube, to ensure that once the wire is placed, the molar still will maintain the ability to rotate, if needed. The operator will then remove the appliance in one piece from the model and will sand blast any excess resin off the bracket and molar tube. The same operator (AN) will instruct the treating resident on how to place the appliance: the molar tube will be placed in the center of the buccal surface of the maxillary first molar and will be light cured. The canine bracket will then be placed so that the bayonet bend is in contact with the mesial surface of the maxillary first molar tube and the wire is passive. The same anchorage protocol and elastic regimen will be utilized in the in-office Class II corrector group.

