10.0 Eligibility Screening*

- 10.1 Describe **screening procedures** for determining subjects' eligibility. Screening refers to determining if prospective participants meet inclusion and exclusion criteria.
 - Include all relevant screening documents with your submission (e.g. screening protocol, script, questionnaire).

Response:

Patients will be screened by their assigned residents according to the protocols set up in the UB Orthodontic Clinic. Each new patient is screened using a specific form supplied by the UB Orthodontic clinic regardless of whether they participate in research or not (I have included a copy of this form with my submission). One research examiner (AN) will review all patient screening forms to determine if the patient meets all necessary inclusion criteria. Once orthodontic records have been taken on the patient by the treating resident, the examiner (AN) will review the records taken (photos, x-rays, digital casts) to confirm that the patient meets all the inclusion criteria in order to participate.

 \square N/A: There is no screening as part of this protocol.

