Models of subjects assigned to the in the in-office fabricated appliance group will be 3D printed, and one operator (AN) will fabricate custom devices for each subject. The buccal surface of the maxillary first molar will be etched for 12s using 35% phosphoric acid, rinsed, dried, and Assure Plus bonding agent will then be applied to the buccal surface of the maxillary first molar, and light cured for 10 s using an LED curing light. A pre-pasted 0.022 Slot MBT second molar minitube that has been modified to have a 2 mm tube length will be placed in the center of the buccal surface of the maxillary first molar and light cured for 40 s. A 0.016x0.022 stainless-steel wire will be roughly sectioned to be longer than the distance from the maxillary first molar to the maxillary canine for ease of placement. Once the wire has been placed through the buccal tube of the molar bracket, it will be marked and a bayonet bend will be placed mesial to the molar tube. A slight curve will be bent into the wire to span the premolars, so that the wire is able to passively rest on the buccal surface of the maxillary canine. The wire will then be used to position the canine bracket, so that the wire rests passively in both the canine and molar brackets. The maxillary canine will be prepared using phosphoric acid etch and assure plus in the same fashion as the molar bracket. A 0.018 MBT maxillary canine bracket will be placed and cured using the stainless-steel wire as a template to ensure passive placement. Once both brackets are placed, the wire will be cut so that a small section of wire remains mesial to the maxillary canine and distal to the maxillary first molar. The wire will then be cinched mesial to the maxillary canine tie-wing. The wire will also be cinched distal to the maxillary first molar, with 2-3 mm of excess wire distal to the maxillary first molar to ensure that the molar can rotate during treatment, if needed. The distance from the mesial opening in the buccal tube of the maxillary first molar to the most distal portion of the canine bracket will be measured, and an closed-coil stainless-steel spring will be sectioned to measure the span from the distal tie-wing of the maxillary canine to the mesial portion of the maxillary molar tube. The wire will be placed into the brackets with the closed-coil spring spanning the molar and canine, and a stainless-steel tie will be used to secure the wire into the canine bracket. The fabricated device will then be removed from the model and the excess cement on the molar and canine pad will be carefully removed prior to cementation in the patient's mouth.

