
For the CMA group Orthocad software will be used by one operator (AN) in order to measure the distance from the center of the buccal surface of the first molar to

the center of the facial surface of the canine (in mm). This measurement will be used to determine the proper size CMA device needed for the study.

Prior to the bonding appointment, digital cases of the mandibular arches of all subjects will be 3D printed, and essix retainers with 2 mm thickness will be fabricated to include an opening on the buccal surfaces of the mandibular first molars for placement of a button to anchor the Class II elastics during treatment.

At the bonding appointment, for both study groups, proper isolation methods will be placed according to the treating resident's preference. Maxillary first molars and canines will be etched using 35% phosphoric acid for 12 s, rinsed, and air thinned using an air water syringe. Assure plus bonding agent will be placed on the molar and canine buccal surfaces, air thinned, and light cured for 10 s. Packable composite will be placed on the molar and canine pads (CMA group) or the maxillary first molar tube and canine bracket (in-office appliance group). The molar pad (for the CMA group) and the first molar bracket (for in-office appliance group) will be positioned onto the center of the buccal surface of the maxillary first molar, and once it has been properly positioned, the canine pad (CMA group) or canine bracket (in-office appliance group) will be placed passively. Excess cement will be removed, and each pad/tube/bracket will be light cured using an LED curing light for 40 s. The mandibular essix retainer will then be placed and adjusted according to patient comfort level. Once the patient is comfortable with the essix retainer, it will be used as a template to mark the buccal surfaces of the mandibular first molars for placement of the buttons. The mandibular first molars will be etched using 35% phosphoric acid for 12 s, rinsed, and air thinned using an air water syringe. Assure plus bonding agent will be placed on the molar and canine buccal surfaces, air thinned and light cured for 10 s. Packable composite will be placed on the pad of the orthodontic buttons, and the buttons will be placed and excess cement will be removed. The buttons will be light cured for 20 s each.

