Isolation will then be removed and the patient will be instructed to wear the essix retainer 24 hours a day and to only take it out to eat and when completing hygiene methods. The patient will be given Force 1 Class II elastics (1/4, 6 oz) and will be instructed on how to place them from either the hook on the canine pad (CMA group) or the hook on the canine bracket (in-office appliance group) to the button on the mandibular first molars. The patient will be instructed to wear the elastics 24 hours a day and to only remove them when eating and completing hygiene methods, and to change elastics daily.

The patient will be seen 1 month later and will be given Force 2 Class II elastics (3/16, 8 oz) and will be instructed to wear them using the same protocol for the remainder of their class II correction. The patient will be evaluated each month until a Class I molar and canine relationship has been obtained.

Once a Class I molar and canine relationship has been obtained, The CMA or in office appliance will be removed, and an intraoral scan and lateral cephalometric radiograph will be taken immediately after removal of the appliance(s) (T1). The

total duration (in months) of Class II correction, starting at the bonding appointment and ending at the T1 appointment will be recorded for each subject.

Superimposition & Data Analysis

Once T0 and T1 records are obtained, lateral cephalometric tracing and measurements will be completed and recorded by one operator (AN). Superimpositions will be constructed using T0 and T1 lateral cephalometric tracings. Initial cephalometric measurement (T0) will be subtracted from final cephalometric measurements (T1) for each value (Please see table in section 12.2 for a complete list of lateral cephalometric measurements and their descriptions).

Intraoral scan data will be collected with an iTero Element 3D Scanner. Digital models will be superimposed using the Best fit method described in a study conducted by Grünheid and Larson. Maxillary model superimpositions will be used to address the difference in maxillary first molar and canine rotational positions before versus after Class II correction (°). Mean values for all measurements (lateral cephalometric and digital model superimposition) will be calculated for each treatment group and statistical analyses will be ran using he Statistical Package for the Social Sciences (SPSS) to compare means.

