One investigator (AN) will be mapping lateral cephalometric radiographs and performing all measurements on patient records, as well as fabricating all inoffice appliances and mandibular essix retainers to reduce heterogeneity. The research examiner and supervisors will be ensuring that the data is good quality and is adequate for analysis. All patient records and data will be encrypted, deidentified and properly stored and secured on our computer network. A Code Key file will be stored in a separate protected drive.

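### The operator who learns each subject's arm by sizing or building the appliance also reads all films and casts with no stated masking, and the same-operator repeat cannot reveal a stable arm-related lean

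*Protocol*

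**What the plan says.** Several sections of the protocol give tasks to the same operator:

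- **Eligibility (10.1).** The examiner "will review the records taken (photos, x-rays, digital casts) to confirm that the patient meets all the inclusion criteria in order to participate".
- **CMA arm (12.1).** The operator measures the molar-to-canine distance for each CMA subject: "This measurement will be used to determine the proper size CMA device needed for the study".
- **In-office arm (6.1, 12.1).** The operator "will fabricate custom devices for each subject" and "will instruct the treating resident on how to place the appliance".
- **Outcome reading (12.1, 19.3).** At the end, "lateral cephalometric tracing and measurements will be completed and recorded by one operator". Section 19.3 gives this person the quality-control role of "performing all measurements on patient records, as well as fabricating all inoffice appliances and mandibular essix retainers to reduce heterogeneity".
- **Reliability (12.1, 19.1).** The same operator repeats 5 cephalograms and 5 casts after two weeks, summarised by intra-class correlation.

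The text closest to masking concerns confidentiality. Section 12.3 says that de-identified measurements go into a spreadsheet. Section 19.3 says that records and data are de-identified and stored, with a code key on a separate drive, but does not say who holds the key. Section 20.0 A first describes the network drive as open to the examiner alone, then says that the examiner and supervising research faculty can open the data. Section 20.1 A names both.

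**The concern.** A single reader is a sound way to keep measurements consistent. It does not make the arms comparable if that reader knows the arm. Every subject passes through an arm-specific task done by this operator: a CMA is sized or an appliance is built. Followed as written, the protocol therefore has the outcomes read by someone who has already learned the allocation.

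Hypotheses 2 and 3 (section 2.2) compare skeletal and dental changes between arms. The film values rest on landmarks that this operator places. If judgement on those landmarks leaned with the arm, the lean would enter the between-arm difference directly, and no later analysis could remove it. The only planned check on measurement is the same-operator repeat.

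**Working it through.** **1. The plan's own figure.** Section 19.2 gives 16 per group for a standardized effect of 1.02366, 80% power and significance level 0.05. For a two-sided two-sample t-test with 30 degrees of freedom, the noncentrality is 1.02366 × √(16/2) = 2.895 and the power is 80.0%. The figure reproduces. It was set for treatment time, not for film or cast measures, and this point does not change it.

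**2. What a lean does to the comparison.** Let δ be the true difference between arms in mean change, and let λ be the average reading lean in the change (T1 minus T0) within an arm. The expected observed difference is

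δ + (λ_CMA − λ_in-office).

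A lean common to T0 and T1 cancels within the subject. A lean in the change that is equal in both arms cancels between arms. Only an arm-related lean in the change remains, and the data give only the sum, so δ and the lean cannot be separated.

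**3. What the repeat can show.** For a given record, write reading 1 = true value + lean + e1 and reading 2 = true value + lean + e2. The difference is e1 − e2, and the lean has dropped out. The intra-class correlation therefore reflects the size of e1 and e2 only. A lean that changed between readings would lower agreement, but a stable one would not. This follows from the algebra and needs no simulation.

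**4. Which measures are exposed.** The tables in section 12.2 list 12 + 3 + 3 + 3 + 6 = 27 film measures. They are not 27 separate exposures. IMPA and L1-MP describe the same angle, the maxillomandibular differential is computed from two other listed lengths, and ANB shares its points with SNA and SNB. Molar and canine rotations come from best-fit superimposition of digital models, so they are probably less exposed than the film landmarks.

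**5. Illustrative size.** The documents give no SD for these measures and no estimate of reader lean, so the shifts below are assumptions. With no true difference, 16 per arm and a two-sided 5% t-test, the noncentrality is d × √(16/2) = d × 2.828:

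| Assumed arm-related shift (SD of change) | Noncentrality | False-positive rate per measure |
|---|---|---|
| 0 | 0 | 5.0% |
| 0.10 | 0.283 | 5.9% |
| 0.25 | 0.707 | 10.5% |
| 0.50 | 1.414 | 27.8% |

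**The case against.** The strongest reply is that the protocol nowhere says the reader will see allocation. It says that all records, not only measurements, are de-identified, and it gives no order for de-identification and reading. This stands in part: the absence of masking is inferred from silence together with the operator's duties. De-identification for storage does not meet the concern, however, because it is not placed before reading and the operator has already handled each subject's records.

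A second reply is that coding the files may achieve little. The operator has seen the T0 records and handled the appliances, T0 and T1 must be paired for superimposition, research time includes orthodontic adjustments for each patient (16.2), and subjects may contact the examiner about a broken appliance (23.2). This stands as a limit on the fix. In its favour, "an intraoral scan and lateral cephalometric radiograph will be taken immediately after removal of the appliance(s) (T1"), so the appliance itself should not be on the T1 film or scan. Feasibility still depends on the bonding sites not giving the arm away.

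A third reply is that these are secondary outcomes of a pilot trial. That limits how serious the point is but does not remove it. A separate SAP would not answer it either, since who reads the records, and knowing what, is a matter of trial conduct.

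**Conclusion.** The point holds as an exposure to bias: one operator learns every arm and reads every film and cast, no masking is stated, and the planned repeat cannot reveal a stable lean. It should be changed before reading starts.

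A reader might infer more than the documents support:

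- **That the readings will be biased.** Nothing shows that a lean occurs, or in which direction. The hypotheses are stated as no difference. The rates of 5.9%, 10.5% and 28% rest wholly on assumed shifts.
- **That landmarks are placed by hand.** The protocol speaks of tracing, landmarking and mapping, without saying whether software assists.
- **That only the operator can reach the data.** Section 20.0 A is unclear on this, and it and section 20.1 A give supervising faculty access.
- **That the primary outcome is affected in the same way.** Duration is computed from bonding and removal dates, not from this operator's readings. Its end point does rest on clinical assessment ("The patient will be evaluated each month until a Class I molar and canine relationship has been obtained"), but the protocol does not name the assessor, and that is a separate question.

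**What to change.** Amend sections 12.1 and 19.3 as follows:

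1. Keep the single operator.
2. Have supervising faculty, who already have data access, code the T0 and T1 files and hold the key where the operator cannot open it.
3. Have the operator read the coded films and casts in random subject order without allocation, either in batches mixing both arms or after the last T1. Pair T0 with T1 only where superimposition needs it.
4. Release the key only after the measurements are locked.
5. State as a limitation that masking is partial, and why.
6. Make section 20.0 A clear on who can open the data and the key.

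If someone already on the team took no part in sizing or fabrication, that person reading the coded files would mask better. The documents do not say whether such a person is available, so this is optional.

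**Cost.** There are no added readings, staff or patient procedures: the same records (at most 32 × 2 = 64 films and 64 casts) are read under codes and in a different order. The added work is some file coding and key-holding by faculty. Waiting for the last T1 would leave about 18 − 6 (enrolment) − 6 (upper end of expected participation) = 6 months, before allowing for records and fabrication. No maximum duration is set, so mixed-arm batches are the safer choice if treatment runs long.

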20.0 Confidentiality*

A. Confidentiality of Study Data

Describe the local procedures for maintenance of confidentiality of study data and any records that will be reviewed for data collection.

1.1 A. Where and how will all data and records be stored? Include information about: password protection, encryption, physical controls, authorization of access, and separation of identifiers and data, as applicable. Include physical (e.g. paper) **and** electronic files.

Response:

The data will be stored within the encrypted and protected network and on the research examiner's University at Buffalo School of Dental Medicine Orthodontic Clinic hard drive. This specific network drive is only accessible by the research examiner using her specific credentials to access the information. The computers which will allow this access will be present in the orthodontic facility where the research will be conducted. There will be password protection to access the computers, as well as physical limitations that are in place to limit access to the facility. In order to access these computers, individuals need physical keys as well as swipe privileges of their ID badges. Subject data will be stored in multiple folders which will also have encryption built in with specific password protection to the data that only the examiner and supervising research faculty will have access to.

1.2 A. How long will the data be stored?

Response: 3 years post-study

20.1 A. Who will have access to the data?

Response: Research Examiner and Supervising Research Faculty

20.2 A. Who is responsible for receipt or transmission of the data?

Response: Research Examiner

20.3 A. How will the data be transported?

Response: Digitally via the encrypted network described above

B. Confidentiality of Study Specimens

Describe the local procedures for maintenance of confidentiality of **study specimens**.

- N/A: No specimens will be collected or analyzed in this research. (Skip to Section 21.0)
- 1.3 B. Where and how will all specimens be stored? Include information about: physical controls, authorization of access, and labeling of specimens, as applicable.

Response:

N/A

1.4 B. How long will the specimens be stored?

Response:

N/A

20.4 B. Who will have access to the specimens?

Response:

N/A

20.5 B. Who is responsible for receipt or transmission of the specimens?

Response:

N/A

20.6 B. How will the specimens be transported?

Response:

21.0	Provisions	to Monitor	the Data	to Ensure	the Safety of	of
Subjects*						

N/A: This study is not enrolling subjects, or is limited to records review procedures only. This section does not apply.

NOTE: Minimal risk studies may be required to monitor subject safety if the research procedures include procedures that present unique risks to subjects that require monitoring. Some examples include: exercising to exertion, or instruments that elicit suicidality or substance abuse behavior. In such cases, N/A is not an acceptable response.

21.1 Describe the plan to periodically evaluate the data collected regarding both harms and benefits to determine whether subjects remain safe.

Response: This study is of minimal risk. Patients' treatment notes will be reviewed after each visit to ensure safety.

21.2 Describe what data are reviewed, including safety data, untoward events, and efficacy data.

Response:

Efficacy data:

Duration of treatment required to obtain a Class I molar and canine relationship (months)

Changes in skeletal and tooth position (mm, °) before versus after Class II correction (Lateral Cephalometric radiographs taken at T0, T1, digital models taken at T0 and T1).

Patient age at T0.

21.3 Describe any safety endpoints.

Response: N/A

21.4 Describe how the safety information will be collected (e.g., with case report forms, at study visits, by telephone calls with participants).

Response: N/A

21.5 Describe the frequency of safety data collection.

Response: N/A

21.6 Describe who will review the safety data.

Response: N/A

21.7 Describe the frequency or periodicity of review of cumulative safety data.

Response: N/A

21.8 Describe the statistical tests for analyzing the safety data to determine whether harm is occurring.

Response: N/A

21.9 Describe any conditions that trigger an immediate suspension of the research.

Response: N/A

